9.9. Protocol Violations/Deviations

This protocol is intended as a FIH study to establish the safety, tolerability, and PK characteristics of KNX100. As such, it is especially important that study sites and investigators conduct the study in accordance with the written protocol, to permit consistent data quality throughout the study.

Every protocol deviation (i.e., any change, divergence, or departure from the study design or procedures defined in the protocol) must be recorded in the subject record (source document) and on the CRF and must be reported to the PI. Protocol deviations will be assessed for significance by the PI, but also will be subject to review by the Sponsor.

Protocol violations (also known as “important protocol deviations”) are a subset of protocol deviations that may significantly impact the completeness, accuracy, and/or reliability of the study data, or that may significantly affect a subject's rights, safety, or well-being. At a minimum, these will include any instances of the following:

- Enrollment of a subject who did not satisfy the entry criteria.
- Failure to withdraw a subject from the study after the subject met withdrawal criteria.
- Subject received the wrong treatment or incorrect dose.

- Subject received an excluded concomitant treatment.
- Failing to collect data necessary to interpret primary endpoints.

The investigator is responsible for promptly notifying the Sponsor or Sponsor representative of any important protocol deviations/protocol violations. For these important deviations, the investigator and Sponsor will determine whether additional reporting is appropriate, considering any local requirements that exceed ICH recommendations.

9.10. Access to Source Documentation

The investigator is responsible for secure storage of completed source documentation and eCRFs until authorized to transfer the documentation to the Sponsor, or to dispose of the documentation. Please refer to [Section 9.6.2](#) for a definition of source documentation.

Study source documentation and CRFs are subject to inspection by the Sponsor, its representatives, the HREC, and Regulatory Authorities, at times of their choosing. The study site must allow study-related monitoring audits and/or inspections when so requested by these authorized persons. Please refer to [Section 9.7](#) for more information on site monitoring audits and inspections.

9.11. Data Generation and Analysis

The Sponsor is responsible for designating appropriate personnel to build and maintain a clinical database appropriate for a pivotal study.

All data from the CRFs will be transferred into a computer database, which will be designed in compliance with applicable conventions for standardized data sets, and with appropriate range checks. Appropriate Sponsor personnel/designees will check the database against the CRF for accuracy. Sponsor personnel/designees will also work with staff at study sites for clarification of data entries as needed (refer to [Section 9.7](#)).

9.12. Retention of Data

Both investigators and the Sponsor are responsible for secure storage of completed CRFs during the conduct of the study.

The Sponsor is responsible for generating backup copies of the CRFs and database and is responsible for securely storing the backups separately from the primary files.

Access to the database will be restricted by password. Computers will be password protected and held in secure monitored facilities.

All data derived from the study will remain the property of the Sponsor. Records must be retained in accordance with the current ICH Guidelines on GCP. All essential study documents including records of subjects, source documents, eCRFs and study drug inventory must be kept in a study specific file.

The site investigator will not dispose of any records relevant to this study without the written permission from the Sponsor and will provide the Sponsor the opportunity to collect such records. The site investigator will notify the Sponsor in writing of their intent to destroy all such material. The Sponsor will have 30 days to respond to the site investigator's notice, and the Sponsor shall have a further opportunity to retain such materials at the Sponsor's expense.

If a site investigator moves, withdraws from an investigation, or retires, the responsibilities for maintaining the records may be transferred to another person who will accept responsibility. Notice of transfer must be made and agreed by the Sponsor.

Per ICH GCP (R2), (ICH Guideline E6), at a minimum the Sponsor-specific essential documents (including subject-specific source documents) should be retained until either of the following is true:

- At least 2 years after the last approval of a marketing application in an ICH region (and until there are no further marketing applications contemplated in ICH regions),
or
- At least 2 years have elapsed since the formal discontinuation of clinical development of the investigational product.

However, source data and other essential documents should be retained for a longer period if required by local regulations.

In Australia, records must be kept for at least 15 years after the completion of a clinical study.

9.13. Financial Disclosure

The investigators and the Sponsor will sign a clinical study agreement prior to the start of the study, outlining the overall Sponsor and investigator responsibilities in relation to the study.

All investigators and the Sponsor will declare any conflicts of interest. If potential conflicts of interest are present, the Sponsor and investigator are jointly responsible for determining appropriate controls to mitigate risks to data integrity at the investigator's site.

Financial Disclosure Statements are required for all investigators on this study worldwide, as required by FDA regulation 21 CFR 54.

9.14. Changes to the Clinical Study Protocol

Changes to the clinical study protocol will be documented in writing. Substantive amendments will usually require submission to the IND and to the relevant HREC for approval or favorable opinion. In such cases, the amendment will be implemented only after approval or favorable opinion has been obtained (refer to [Section 9.2](#)).

Minor (non-substantial) protocol amendments, including administrative changes, will be filed by the Sponsor and at the site. They will be submitted to the relevant HREC or to regulatory bodies only where requested by pertinent regulations. Any amendment that could affect the subject's agreement to participate in the study requires additional informed consent prior to implementation, following the process as described in [Section 6.1](#) and [Section 9.4](#).

9.15. Disruption Due to Coronavirus Disease 2019 (COVID-19) Pandemic

If a clinical site or investigator experiences disruption due to COVID-19 (or other natural disaster), a shortened list of assessments may be implemented as an immediate safety measure to ensure at least safety, primary, and key secondary endpoints are captured for any dosed subject. Assessments may be performed by telephone if possible.

If a subject develops COVID-19, this will be reported and followed as an AE per [Section 6.17](#). The investigator will follow the standard operating procedures for the site as well as local, regional, and national guidelines for COVID-19. Investigators should use clinical judgement as to whether a subject should continue, temporarily stop, or permanently withdraw from the study.

9.16. Publication and Data Disclosure Policy

By signing the study protocol, the investigator agrees with the use of the results of the study for the purposes of national and international registration, publication, and information for medical and pharmaceutical professionals. Regulatory Authorities will be notified of the investigator's name, address, qualifications, and extent of involvement.

All data generated from this program are the property of the Sponsor and shall be held in strict confidence along with all information furnished by the Sponsor. Independent analyses and/or publication of these data by the investigator or any member of his/her staff are not permitted without prior written consent of the Sponsor. An investigator may not publish any data (poster, abstract, paper, etc.) without having consulted with the PI and Sponsor in advance and having received a written approval for such a publication.

Further details on the publication process are provided in individual contractual agreements signed by the investigators and the Sponsor.

Appendix 1 Schedule of Assessments - SAD

	Screening	Treatment			Follow Up/ ET/EOS ¹
Study Day	-28 to -2	-1	1	2 ²	7 (±2)
Informed Consent	X				
Inclusion/Exclusion Criteria ³	X	X			
Randomization ⁴		X			
Height and BMI	X				
Medical History and Demographics	X				
Physical and Neurological Exam ⁵	X	X	X	X	X
Vital Signs ⁶	X	X	X	X	X
Laboratory Tests ⁷					
Serology	X				
Hematology	X	X	X	X	X
Serum Chemistry	X	X	X	X	X
Urinalysis ⁸	X	X	X	X	X
Coagulation	X	X	X	X	X
Pregnancy Test ⁹	X				X
Drug of Abuse Screening ¹⁰	X	X			
Alcohol Breath Test	X				
Study Drug Administration ¹¹			X		
PK Assessments ¹²			X	X	
Biomarker Sample ¹³		X	X		X
EEG ¹⁴	X		X	X	
12-Lead ECG ¹⁵	X	X	X	X	X
Adverse events	X	X	X	X	X

	Screening	Treatment			Follow Up/ ET/EOS ¹
Concomitant Medications	X	X ³	X	X	X
Inpatient Component ¹⁶	X	X	X	X	

Abbreviations: BMI = body mass index; ECG = electrocardiogram; EEG = electroencephalography; ET = early termination; EOS = end of study; PK = pharmacokinetics; SAD = single ascending dose.

¹ All subjects will be required to attend an ET/EOS visit, even if they have withdrawn or been removed from the study. For completed subjects, this will be at Day 7.

² For sentinel subjects this will include a follow up phone call at 48 hours.

³ Confirmation of eligibility based on inclusion/exclusion criteria.

⁴ Randomization to occur after confirmation of eligibility on Day -1 and prior to dosing on Day 1.

⁵ An abbreviated neurological examination will be undertaken to include: light touch/power in limbs, brief cranial nerve examination and recording of any other abnormal movements; to occur on Day-1, Day 1 predose and at 30 minutes (\pm 15 minutes) postdose, and Day 2. Physical and neurological examination on Day 2 should be performed pre-discharge.

⁶ Vital signs collection includes systolic and diastolic blood pressures, pulse rate and body temperature which will be measured with the subject to be seated or semi-supine after resting for at least 3 minutes. Vital signs also include respiratory rate, continuous pulse oximetry and saturated oxygen, which will be undertaken via telemetry within 2 hours predose and at 30 hours (\pm 30 minutes) after dosing. Measurements of all vital signs will be recorded within 1 hour predose, and at 30 minutes, 1-, 1.5-, 2-, 4-, 6-, 8-, 12-, 24- and 30-hours postdose (\pm 15 minutes). Peak flow measurement will also be undertaken within 1 hour predose as well as at 1-, 2-, and 4-hours (\pm 15 minutes) postdose. The highest of 3 peak flow measurements, at each timepoint, shall be recorded.

⁷ Subjects should fast overnight prior to collection of laboratory tests at Screening. The Day 1 laboratory tests will be undertaken at 1 hour postdose (\pm 15 minutes) and at 24 hours (\pm 15 minutes) postdose (Day 2).

⁸ The Day 1 urinalysis tests will be undertaken at 1-hour postdose (\pm 60 minutes) and at 24 hours (Day 2) (\pm 60 minutes) postdose.

⁹ Serum pregnancy test at Screening and End of study visit. A urine pregnancy test will be conducted in women of child-bearing potential on admission to unit on Day -3.

¹⁰ Test may be repeated if required.

¹¹ Each subject will receive study drug based on randomization (placebo or KNX100), after a 10 hour fast.

¹² Please refer to [Appendix 3](#) for information related to PK assessments and sampling times.

¹³ Plasma samples for biomarker analyses will be collected predose (Day -1), on Day 1 at 1-hour postdose (\pm 15 minutes), and at EOS/EOT.

¹⁴ EEG: Please refer to [Appendix 3](#) for information related to EEG assessments.

¹⁵ Please refer to [Appendix 3](#) for information related to ECG assessments which will be performed in triplicate. The timing and number of ECGs may be altered, depending on the emerging PK and safety profile. Additional ECGs should also be collected if a subject experiences a cardiac adverse event.

¹⁶ Participants will be admitted to the Phase 1 unit on Day -3 so they can sleep for 4 hours prior to undertaking their sleep deprived EEG on Day -2, through to 30 hour testing on Day 2.

Appendix 2 Schedule of Assessments – MAD

	Screening	Treatment									ET/EOS ¹
Study Day	-28 to -2	-1	1	2	3	4	5	6	7	8 ²	14 (± 2)
Informed Consent	X										
Inclusion/Exclusion criteria ³	X	X									
Randomization ⁴		X									
Height and BMI	X										
Physical and Neurological Exam ⁵	X	X	X	X	X	X	X	X	X	X	X
Gastrointestinal Symptoms ⁶	X	X	X	X	X	X	X	X	X	X	X
Vital Signs ⁷	X	X	X	X	X	X	X	X	X	X	X
Concomitant Medications	X	X	X	X	X	X	X	X	X	X	X
Laboratory Tests ⁸											
Serology	X										
Hematology	X	X	X	X		X		X	X	X	X
Serum Chemistry	X	X	X	X		X		X	X	X	X
Urinalysis	X	X	X	X		X		X	X	X	X
Coagulation	X	X	X	X		X		X	X	X	X
Pregnancy Test ⁹	X	X									X
Drug Abuse Screening	X	X ¹⁰									
Alcohol Breath Test	X	X ¹⁰									
Study Drug Administration ¹¹			X	X	X	X	X	X	X		
PK Assessments ¹²			X			X ¹²			X		
Biomarker Sample ¹³		X	X	X	X				X		X

Study Day	Screening	Treatment									ET/EOS ¹
	-28 to -2	-1	1	2	3	4	5	6	7	8 ²	14 (± 2)
12-Lead ECG ¹⁴	X	X	X	X	X	X	X	X	X		X
EEG ¹⁵	X		X	X	X	X	X	X	X	X	
C-SSRS ¹⁶	X					X			X		
Adverse Events	X	X	X	X	X	X	X	X	X	X	X
Inpatient component ¹⁷	X	X	X	X	X	X	X	X	X	X	

Abbreviations: BMI = body mass index; C-SSRS = Columbia Suicide Severity Rating Scale; ECG = electrocardiogram; EEG = electroencephalography; EOS = end of study; ET = end of treatment; PK = pharmacokinetics; MAD = multiple ascending dose; SAD = single ascending dose.

¹ All subjects required to attend an ET/EOS visit, even if they have withdrawn or been removed from the study.

² Day 8 is 24-hours (± 1 hour) after administration of the last morning dose. This visit will be used to collect the “24-hour” assessments.

³ Confirmation of eligibility based on inclusion/exclusion criteria.

⁴ Randomization to occur after confirmation of eligibility on Day -1 and prior to the first dose on Day 1.

⁵ An abbreviated neurological examination will be undertaken to include: light touch/power in limbs, brief cranial nerve examination up to 1 hour prior to the first dose and at 30 minutes (± 15 minutes) post morning dose.

⁶ An assessment of bowel movements including any incidence of constipation or changes in bowel habits will be conducted daily. On Day -1 and Day 1, the gastrointestinal screening assessments will be conducted as part of physical examinations. On Days 2, 3, 4, 5, 6, 7, 8 and Day 14, a gastrointestinal questionnaire will be administered within 30 minutes prior to morning dosing.

⁷ Vital signs will be measured with the subject to be seated or semi-supine after resting for at least 3 minutes. Measurements will include systolic and diastolic blood pressures, pulse rate, body temperature, respiratory rate, saturated oxygen and pulse oximetry which will be recorded via telemetry within 2 hours predose and at 2 hours postdose (± 15 minutes). Peak flow measurement will also be undertaken within 1 hour predose as well as at 1-, 2-, and 4-hours (± 15 minutes) postdose. The highest of 3 peak flow measurements, at each timepoint, shall be recorded. For MAD Cohort 3, vital signs, telemetry, and peak flow measurements will be recorded following each dose as per the schedule above.

⁸ Laboratory tests will be undertaken as depicted above. The Day 1 laboratory tests will be undertaken 1 hour post morning dose (± 15 minutes).

⁹ A serum pregnancy test will be undertaken at screening and End of Study visit. A urine pregnancy test will be conducted in women of child-bearing potential on admission (Day -3).

¹⁰ Drug abuse screening and alcohol breath test will be conducted at admission (Day -3).

¹¹ Subjects in Cohorts 1 and 2 of the MAD study phase will be dosed daily for 7 days at approximately the same time each day. Each subject will receive study drug based on randomization (placebo or KNX100), after a 10 hour fast. Subjects will remain fasted until 2 hours (±15 minutes) post study drug administration.

Subjects in Cohort 3 of the MAD study phase will be dosed twice daily (b.i.d) with doses administered approximately 8 hours (\pm 30 minutes) apart. The first dose will be administered following a 10 hour overnight fast, and subjects will remain fasted until 2hours (\pm 15 minutes) post study drug administration. Subjects will be required to fast 2 hours (\pm 15 minutes) prior to administration of the second dose of study drug and will remain fasted until 2hours (\pm 15 minutes) post study drug administration.

¹²Please refer to [Appendix 3](#) for information related to PK assessments and sampling times. The timing and number of PK samples may be altered depending on emerging data and safety profile. Please note, Day 4 predose sample is not required for Cohort 3.

¹³ Plasma samples for biomarker analyses will be collected predose (Day -1), and 1 hour post morning dose (\pm 15 minutes) on Days 1, 2, 3, 7 and at the ET/EOS visit.

¹⁴ Please refer to [Appendix 3](#) for information related to ECG assessments. ECGs will be undertaken in triplicate. The timing and number of ECGs may be altered, depending on the emerging PK and safety profile. ECGs should also be collected if a subject experiences a cardiac adverse event.

¹⁵ EEG: Please refer to [Appendix 3](#) for information related to EEG assessments.

¹⁶ C-SSRS: will be administered predose at screening and then within 4 hours post the morning dose on Days 4 and 7.

¹⁷ Subjects will be admitted to the unit on Day -3 to undertake their sleep deprived EEG. Subjects will remain in the unit during the entire dosing phase and be discharged after collection of Day 8 assessments.

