6.4. Physical and Neurological Examinations

A medical assessment will be completed by the principal investigator (PI) or a study physician at study entry, and at any early withdrawal visits. The primary purpose of the medical assessment at study entry is to confirm the subject's suitability to enroll in the study.

The physical examination will include height (screening only), body weight, and an evaluation of the head, eyes, ears, nose, and throat, and the cardiovascular, dermatological, musculoskeletal, respiratory, gastrointestinal, and neurological systems. Record any abnormality identified prior to administration of study medication as medical history.

Any clinically significant, new, or worsened abnormalities that occur after administration of study medication should be recorded as AEs. Additional parameters may be assessed as indicated by any subject symptoms.

Abbreviated physical examinations performed throughout the study should be symptom-directed.

Neurological examination shall include assessment of cranial nerves, motor, sensation, coordination, reflexes, and gait. Abbreviated neurological examinations performed throughout the study include light touch/power in limbs and brief cranial nerve examination.

Findings will be recorded as normal/abnormal for each parameter with additional description as indicated. All abnormal, clinically significant, findings will be considered AEs.

Please refer to the Schedule of Assessments (SOA) in [Appendix 1](#) and [Appendix 2](#) for details regarding timing for assessments.

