6.6. Gastrointestinal Symptoms

Changes in gastrointestinal function will be monitored during the MAD part of the study. Bowel movements, such as constipation, and any change in bowel habits as reported by study subjects will be recorded daily during the dosing period.

Please refer to the SOA in [Appendix 2](#) for details regarding timing for these assessments.

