5.2 General Definitions

Variable	Definition
Study Day	
 • Study Day = date of interest – treatment start date + 1, when the date of interest \geq treatment start date; • otherwise, Study Day = date of interest – treatment start date. 
Note: if either date is missing, Study Day calculations will not be performed. Should imputation be performed, then Study Day may be computed, where appropriate.

Baseline	
For ECG data, baseline is defined as the average of up to three measurements taken at the pre-dose timepoint on the Day 1 Visit if available; otherwise, baseline is defined as the last single tracing measurement taken prior to the first dose of study treatment.
 
For EEG data, baseline is defined as the assessment collected at the Screening Visit (Day -2) in which the patient was in a sleep deprived state.
 
For all other endpoints, baseline is defined as the last non-missing value collected prior to receiving the first dose of study treatment (based on date and time of administration as applicable). For endpoints with both planned pre-dose and post-dose timepoint assessments on Day 1, only pre-dose assessments will be considered as a candidate for baseline. For MAD Cohort 3, vital signs

	assessments on Day 1 associated with the second dose (i.e., evening) will not be considered as a candidate for baseline.
Post-baseline	Defined as values collected after receipt of the first dose of study treatment (based on date and time of administration as applicable)
Change from Baseline	Defined as: Post-baseline value – Baseline value
Duration on Study (in days)	End of study date – randomization date + 1
BMI (kg/m ²)	BMI is collected in the clinical database
Age (yr)	Age is collected in the clinical database
Study Completion	Defined as attendance at the End of Study (EOS) Visit.

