6.4.7 Gastrointestinal Symptoms

Frequency and percentage of subjects in Part B (MAD) cohorts experiencing any gastrointestinal symptoms will be summarized by study part and cohort at each visit and any post-baseline. All gastrointestinal symptom assessment results recorded on the CRF will be presented in by-subject data listings.

Gastrointestinal symptom assessments will not be performed for Part A (SAD) subjects.

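### In Part B, gastrointestinal status moves from physical examination (Day -1 and Day 1) to questionnaire (Day 2 onward), so a within-arm rise cannot be told apart from the change of method

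*Protocol*

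**What the plan says.** Gastrointestinal (GI) symptoms are assessed only in Part B (SAP 6.4.7). Protocol 6.6 sets out to monitor changes in GI function and says that "any change in bowel habits as reported by study subjects will be recorded daily during the dosing period"; it mentions no change of method.

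The method is in footnote 6 of Protocol Appendix 2. The content is the same throughout: "An assessment of bowel movements including any incidence of constipation or changes in bowel habits will be conducted daily". The way of collecting it is not. On Day -1 and Day 1, "the gastrointestinal screening assessments will be conducted as part of physical examinations". For Days 2 to 8 and Day 14, "a gastrointestinal questionnaire will be administered within 30 minutes prior to morning dosing". The grid also marks GI symptoms at Screening, but the footnote gives no method for that visit.

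On examinations in general, Protocol 6.4 says: "Abbreviated physical examinations performed throughout the study should be symptom-directed".

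SAP 6.4.7 plans one summary: the number and percentage of Part B subjects "experiencing any gastrointestinal symptoms will be summarized by study part and cohort at each visit and any post-baseline". It plans no change from baseline, no shift table and no new-or-worse row, and it does not mention the two methods. Under SAP 5.2, for endpoints other than ECG and EEG, "baseline is defined as the last non-missing value collected prior to receiving the first dose of study treatment".

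**The concern.** A safety measure meant to show change needs a starting value taken in the same way as the later values. Here the method changes between Day 1 and Day 2, almost exactly when dosing starts. A structured form may prompt complaints that an examination would not, above all if that examination is abbreviated and follows up only what the subject raises. Someone reading across the visit columns of the SAP 6.4.7 table for a KNX100 cohort would see the drug effect, if any, and the effect of the new form as one number.

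The any-post-baseline count has a related weakness. It counts any symptom recorded after the first dose, so a mild complaint that predates dosing but is first written down on the Day 2 form counts the same as a new one.

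**Working it through.** The plan states no figure for this measure, so there is nothing to reproduce. The check has three parts.

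**1. Which method supplies baseline and post-baseline values?**

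- Day -1: examination. Day 1: examination, time relative to the dose not given. Days 2-8 and 14: questionnaire. Screening: not stated.
- If the Day 1 assessment is pre-dose, the SAP 5.2 baseline is the Day 1 examination value. If it is post-dose, baseline is the Day -1 examination value. The Day 1 value then becomes post-baseline, and the any-post-baseline count pools both methods.
- Even if the questionnaire were used at Screening, the last-value rule would pass over it in favour of the later examination, unless both examination values were missing.

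**2. How large could the effect of the switch be?** The documents give no symptom rates or detection rates, so these inputs are assumed: true symptom rate p = 10-30%; detection by examination s_E = 30% or 50%; detection by questionnaire s_Q = 90%.

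Recorded rise within an arm with no drug effect = p × (s_Q − s_E):

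| p | s_E = 30% | s_E = 50% |
|---|---|---|
| 10% | 0.10 × 0.60 = 6 points | 0.10 × 0.40 = 4 points |
| 20% | 0.20 × 0.60 = 12 points | 0.20 × 0.40 = 8 points |
| 30% | 0.30 × 0.60 = 18 points | 0.30 × 0.40 = 12 points |

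If both methods detect 90%, the rise is 0.

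Now add an assumed 20-point drug effect d. The within-KNX100 rise is (p + d) × s_Q − p × s_E. It runs from 0.30 × 0.9 − 0.10 × 0.5 = 22 points to 0.50 × 0.9 − 0.30 × 0.3 = 36 points. The same-visit difference from placebo is (p + d) × s_Q − p × s_Q = d × s_Q = 0.20 × 0.9 = 18 points in every case, and 0 when d = 0. The switch cancels out of the comparison between arms.

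**3. How precise is that comparison?** Three planned Part B cohorts at 6 KNX100 and 2 placebo give 18 and 6 subjects. The 95% half-width is 1.96 × √[a(1−a)/n + b(1−b)/6], where a and b are the recorded KNX100 and placebo rates (normal approximation, crude at this size).

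- a = 0.36, b = 0.18 (p = 20%): 49 points against one cohort of 6; 38 points against all 18.
- a = 0.45, b = 0.27 (p = 30%): 53 points and 42 points.
- With 0 of 6 placebo subjects symptomatic, the exact two-sided 95% upper limit is 1 − 0.025^(1/6) = 45.9%.

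**A side finding.** Footnote 6 times the questionnaire before morning dosing on Days 8 and 14 as well, but Appendix 2 shows dosing only on Days 1 to 7.

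**The case against.** The strongest reply is that randomized, blinded placebo subjects follow the same schedule. From Day 2 both arms are asked in the same way at the same visit, so that comparison carries no bias from the switch. Protocol 3.2 names the matching placebo as the means of evaluating treatment-related effects. SAP 6.4.7 plans no change from baseline, so the confounded contrast is one that a reader might make, not one the plan makes. All of this stands. A reader might infer that every rise after dosing is contaminated, or that each subject's own baseline is the main control; the documents support neither. Six placebo subjects protect only weakly, but that is the limited precision of a small descriptive study and not a bias.

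The reply can go further. The items are the same on every day and are subject-reported, so asking them during an examination may detect as much as the form does. The questionnaire is not in the documents, so this cannot be settled; the 4 to 18 points depend on assumed detection rates. Nor is it right to infer that change cannot be seen at all. The items ask directly about changed bowel habit. Adverse events must be new or worse than at Screening (Protocol 6.17, SAP 6.4.1), and clinically significant GI disorder is excluded (Protocol 4.3).

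A reader might also size the problem by the chance that at least one of six KNX100 subjects reports a background symptom: 1 − 0.9^6 = 47% at an assumed rate of 10%, and 1 − 0.8^6 = 74% at 20%. The arithmetic is correct, but it has no term for a change of method and would be the same with one questionnaire throughout. It does not measure this weakness.

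One practical point remains on the other side. Cohort review works on blinded data (Protocol 5.3.4 and 9.8.1), so the arms cannot be compared at that stage. Against that, GI questionnaire data are not named in the minimum review list in 5.3.4.

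**Conclusion.** The point holds as a minor weakness that is cheap to repair. The change of method is explicit in Appendix 2, it falls at the start of dosing, and neither document addresses it. Two things follow. A within-arm rise from Day -1/Day 1 to Day 2 onward cannot be attributed to drug alone. And the any-post-baseline count in SAP 6.4.7 cannot separate pre-existing from new symptoms.

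The size is unknown: 4 to 18 points under the assumed rates, and nothing if the two methods detect equally well. GI symptom counts are not a named endpoint in Protocol 8.5, and GI adverse events are captured separately, so the trial's main safety conclusions do not depend on this.

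It would also be too strong to conclude that no subject completes a questionnaire before the first dose. Footnote 6 lists none, which makes it likely, but the Screening method is unstated.

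**What to change.** - **Protocol, Appendix 2, footnote 6:** give the same GI questionnaire on Day -1 or pre-dose on Day 1. State the method at Screening and whether the Day 1 assessment precedes the dose. Correct the timing wording for Days 8 and 14.
- **SAP 6.4.7:** name that questionnaire as the GI baseline, and tabulate symptoms new or worse than it beside the any-symptom counts.
- **If Part B data are already collected:** state in SAP 6.4.7 the method used at each visit, show Day -1 and Day 1 separately from the questionnaire visits, and rest interpretation on same-visit comparison with Part B placebo, noting that only 6 such subjects are planned.

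The cost is one short form per Part B subject, at a time when subjects are already in the unit and a GI assessment is already scheduled, plus one table row. A matched baseline would remove symptoms already present before dosing. It would not remove new background symptoms, and it would not improve the precision of the placebo comparison.
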